Worsening of hypertension	
In a dog cardiovascular study, single oral doses of daprodustat (up to 90 mg/kg) did not produce effects on blood pressure.
 
Marketed rhEPO and its analogues have been associated with risks related to uncontrolled hypertension, including the need for initiation of
	
 • Specific eligibility criteria related to current uncontrolled hypertension are outlined in Section 6.2 • Blood pressure will be closely monitored

Potential Risk of Clinical Significance	Summary of Data/Rationale for Risk	Mitigation Strategy
	
or increases in antihypertensive therapy when used in patients with anemia of CKD (i.e. 25% Epogen, 27% Mircera, and 40% Aranesp treated patients with renal anemia required initiation or increase in their anti-hypertensive medications; hypertensive encephalopathy and seizures have been reported. The contribution of rhEPO-associated hypertension to the unfavourable effects on cardiovascular outcomes remains uncertain).
 
Integrated AE data from clinical trials with daprodustat [including 2 global phase 2b studies (24-week treatment duration) and 2 Japanese phase 3 studies (52-week treatment duration)]:
 
 ○ The majority (>90%) of participants had a baseline history of hypertension. ○ No meaningful difference was seen between treatment groups in AEs (preferred term) of “hypertension” [29/688 (4%) daprodustat vs. 19/404 (4%) rhEPO; 0.91 relative risk (RR) (95% confidence interval: 0.5, 1.67)] or “blood pressure increased” [16 (2%) daprodustat vs. 7 (2%) rhEPO; RR 1.22 (0.48,3.11)]. Results were not substantively different between non-dialysis and haemodialysis participants. ○ Although no clinically meaningful changes in blood pressure were observed, participants in both treatment groups required increases in anti-HTN medications: 
 ○ In the 24-week global phase 2b studies, 25/170 (15%) of ND participants receiving daprodustat vs. 18/80 (14%) control and 22/177 (12%) of HD participants receiving daprodustat vs. 2/39 (5%) control. ○ In the 52-week Japan phase 3 studies, 57/149 (38%) of ND participants receiving daprodustat vs. 68/150 (45%) rhEPO and 51/136 (38%) of HD participants 	
throughout the dosing period as outlined in the Schedule of Activities (Section 2)
 
 • Instream monitoring of safety data by internal safety review team.

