
 To compare daprodustat to placebo on measures of iron status, rhEPO and Transfusion use 	
 Observed and change from baseline in hepcidin, ferritin, transferrin saturation, serum iron, total iron binding capacity (TIBC) Average monthly oral iron dose/participant (mg) to Week 28 N (%) of participants who reduced oral iron supplementation from baseline N (%) of participants requiring IV iron each month. Average monthly IV iron dose/participant (mg) to Week 28 Time to first IV iron, rhEPO and Transfusion use

Objectives	Endpoints
	
 Summary of frequency and dose of IV iron

 To compare daprodustat to placebo on renal function 	
 Estimated Glomerular Filtration Rate (eGFR) observed and change from baseline Serum creatinine observed and change from baseline N (%) transitioning to dialysis

 Evaluate the dose adjustment schemes 	
 Assigned dose by visit Most recent dose prior to Week 24, Week 28 and End of Treatment Maximum achieved dose Number (%) of participants with 0, 1, 2 or >2 dose adjustment Mean number of dose adjustments Time dose held for Hgb\geq13 g/dL

 To compare daprodustat to placebo on BP medication changes 	
 N (%) of subjects who had no change, an increase or a decrease in the number of BP medications from baseline to week 28 or final visit for non-completers

 To compare daprodustat to placebo on the severity and change in symptoms 	
 N(%) of participants within each PGI-C symptom change.

 To compare daprodustat to placebo for improving physical activity (actigraphy) 	
 Change in percent and mean number of hours of daily activity from baseline. Change in percent sleep efficiency from baseline.

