7.8. Concomitant Therapy

Any medication or vaccine (including over-the-counter or prescription medicines, vitamins, and/or herbal supplements) that the participant is receiving at the time of enrollment or receives during the study must be recorded along with:

- reason for use
- dates of administration including start and end dates
- route of administration

For any therapy related to anemia and hypertension, including iron, the following additional information should also be captured:

- Dosage information including:
 - Dose and frequency
 - Formulation
 - Reason for addition or termination
 - Change in dose and reason for change in dose

The use of rescue medications is discussed in Section [7.7.2](#).

The Medical Monitor should be contacted if there are any questions regarding concomitant or prior therapy.

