| 
 • Assigned dose by visit • Most recent dose prior to Week 24, Week 28 and end of study treatment • Maximum achieved dose • Number (%) of participants with 0, 1, 2, or >2 dose adjustments during the treatment period • Mean and median number of dose adjustments during the treatment period • Time dose held for Hgb ≥ 13 g/dL during the treatment period |
| Planned Exploratory Displays |
| 
 • The assigned dose by visit will be summarized using mean, standard deviation, minimum, P25, median, P75, and maximum. • The most recent dose prior to Week 28 and end of treatment will be summarized by the number and percentage of participants at each dose level. • The maximum achieved dose will be summarized using mean, standard deviation, minimum, P25, median, P75, and maximum. • The number and percentage of participants with 0, 1, 2, or >2 dose adjustments will be summarized by treatment group during the treatment period. This summary will be produced twice – the first time counting all dose adjustments, including adjustments related to periods of dose holds (i.e., no study treatment is given), the second time excluding dose adjustments related to periods of dose hold. • The time (in days) that study treatment was withheld for Hgb values ≥ 13 g/dL per participant will be summarized using mean, standard deviation, minimum, P25, median, P75, and maximum during the treatment period. |

Blood Pressure

| Endpoint / Variables |
|--|
| 
 • N (%) of subjects who had no change, an increase or a decrease in the number of BP medications from baseline to week 28 or final visit for non-completers |
| Planned Exploratory Displays |
| 
 • Summary table listing the N (%) of subjects in each treatment group who have no change, an increase or a decrease in the number of BP medications from baseline to week 28 or final visit for non-completers. Summary to include: 
 ○ For subjects who have no change in the number and class of blood pressure medications taken between baseline and Week 28. ○ For subjects who have the same number of blood pressure medications taken at baseline and Week 28, but a change in the class ○ For subjects who have an increase in the number of blood pressure medications taken between baseline and Week 28 ○ For subjects who have a decrease in the number of blood pressure medications taken |

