CONFIDENTIAL

205270

between baseline and Week 28

- If a subject has an increase and then a decrease (or vice versa) in the number of blood pressure medications taken, for reporting purposes that subject will be categorized as having an increase in the number of medications and they will appear in the increase table above.

Severity and Change in Symptoms

| |
|--|
| Endpoint / Variables |
| 
 • N(%) of participants within each PGI-C symptom change. |
| Planned Exploratory Displays |
| 
 • Scoring for the PGI-S is outlined in Section 10.6.5. The number and percentage of participants in each PGI-C category at each scheduled on treatment visit will be summarized. |

Physical Activity (Actigraphy)

| |
|---|
| Endpoint / Variables |
| 
 • Change in percent and mean number of hours of daily activity from baseline. • Change in percent sleep efficiency from baseline. • Wear time of actigraphy device |
| Planned Exploratory Displays |
| 
 • The on treatment percentage of daily light, moderate, vigorous, very vigorous, and moderate to vigorous physical activity (MVPA) activity at each Actigraphy collection period will be defined as the average percentage of daily light, moderate, vigorous, very vigorous, and MVPA activity during the collection period. • The on treatment mean number of hours of daily light, moderate, vigorous, very vigorous, and MVPA activity at each Actigraphy collection period will be calculated as the average number of hours of daily light, moderate, vigorous, very vigorous, and MVPA activity during the collection period. • The on treatment percentage and mean number of daily light, moderate, vigorous, very vigorous, and MVPA activity, the percent sleep efficiency, and wear time will be summarized using mean, standard deviation, minimum, P25, median, P75, and maximum by treatment group at all Actigraphy collection periods. • Change from baseline in the on treatment percentage and mean number of daily light, moderate, vigorous, very vigorous, and MVPA activity, the percent sleep efficiency, and wear time will be summarized using mean, standard deviation, minimum, P25, median, P75, and maximum by treatment group at all Actigraphy collection periods. |

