- BP exacerbations will be defined as (≥ 25 mmHg increase from baseline or SBP ≥ 180 mmHg or DBP ≥ 15 mmHg increase from baseline or DBP ≥ 110 mmHg) and grouped by type as follows:
 - BP exacerbations
 - SBP exacerbations
 - ≥ 25 mmHg increase from baseline or
 - SBP ≥ 180 mmHg
 - SBP ≥ 180 mmHg and baseline SBP < 180 mmHg (including subjects with a missing baseline SBP)
 - SBP ≥ 180 mmHg and baseline SBP ≥ 180 mmHg
 - DBP exacerbations
 - ≥ 15 mmHg increase from baseline or
 - DBP ≥ 110 mmHg
 - DBP ≥ 110 mmHg and baseline DBP < 110 mmHg (including subjects with a missing baseline DBP)

CONFIDENTIAL

205270

| Blood Pressure Endpoints |
|---|
| 
 ○ DBP \geq 110 mmHg and baseline DBP \geq 110 mmHg 
Notes:
 
 ● BP values used to assess BP exacerbations must be on-treatment (see Section 10.4.1), unless otherwise specified. ● BP values used to assess BP exacerbations can be scheduled or unscheduled. ● For visits where BP is measured in triplicate, the average of the 3 BP values will be used to assess BP exacerbations. ● For subjects who start in-clinic dialysis during the study, BP exacerbations identified using post-dialysis BP values will be used in summaries and analyses of BP exacerbations, unless otherwise specified. ● Subjects with multiple exacerbation events on the same calendar date for each type defined above are considered to have one exacerbation event for event counts by type. For example, a subject with a SBP and a DBP exacerbation on the same date would count in each of the SBP and DBP types, but would only count as one BP exacerbation event in the total BP exacerbation type. |
| MAP |
| 
 ● $MAP = [(2*DBP)+SBP]/3$ |

| Imputation |
|---|
| HGB |

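### SAP 7.4.2 reports a fall and return in the number of BP drugs as an increase, although the count never exceeded baseline

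*SAP*

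**What the plan says.** Protocol section 4 sets the exploratory objective "To compare daprodustat to placebo on BP medication changes". The endpoint in both documents is the number and percentage of subjects with no change, "an increase or a decrease in the number of BP medications from baseline to week 28 or final visit for non-completers".

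SAP 7.4.2 (Blood Pressure) sorts subjects into four groups: same number and class, same number but different class, more drugs, and fewer drugs. The first group is those who "have no change in the number and class of blood pressure medications taken between baseline and Week 28". A closing rule covers subjects whose count moves both ways. After naming a rise followed by a fall, it continues: "or vice versa) in the number of blood pressure medications taken, for reporting purposes that subject will be categorized as having an increase". Table 2.126 is the only planned display of BP-medication changes.

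Protocol 7.8 requires extra detail for hypertension therapy, including "Change in dose and reason for change in dose".

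**The concern.** The endpoint is a comparison of two time points. The closing rule is triggered by the path between them and sets no condition on where the path ends or whether it ever went above baseline. A subject who drops a drug and later resumes it, or resumes only part of what was stopped, is reported as having more BP medication than at baseline.

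The row matters because worsening of hypertension is an adverse event of special interest that Protocol 3.3.1 says the existing data cannot refute. The same section notes that "participants in both treatment groups required increases in anti-HTN medications" although no clinically meaningful change in BP was seen. A count of treatment increases is thus one way to see an effect that treatment has masked. Adding subjects who never went above baseline makes that count harder to read.

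**Working it through.** Neither document gives an expected rate, sample size or power for this endpoint, so there is no stated figure to reproduce. The check applies the rules to example paths.

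**Step 1. Rules.** Let c0 be the baseline count and cL the last count.
- SAP, literal: increase if the path contains both a rise and a fall, or if cL > c0; decrease if cL < c0 with no rise; otherwise same number.
- Endpoint definition: compare cL with c0.
- Proposed: increase if any post-baseline count exceeds c0; otherwise compare cL with c0.

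**Step 2. Results.**

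| Path | cL − c0 | SAP, literal | Endpoint definition | Proposed |
|---|---|---|---|---|
| 2-2 | 0 | same | same | same |
| 2-3 | +1 | increase | increase | increase |
| 3-2 | −1 | decrease | decrease | decrease |
| 2-3-2 | 0 | increase | same | increase |
| 2-3-1 | −1 | increase | decrease | increase |
| 3-2-3 | 0 | **increase** | same | same |
| 3-1-2 | −1 | **increase** | decrease | decrease |
| 4-2-3 | −1 | **increase** | decrease | decrease |

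The paths 2-3-2 and 2-3-1 also depart from the two-point definition, but the subject did go above baseline, so calling them increases is a defensible cautious choice. The last three paths never exceeded baseline.

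**Step 3. What the row becomes.** A net increase needs at least one upward step, and every mixed path contains one. Under the literal rule the increase row is therefore everyone with any upward step after baseline. One side effect is that a subject who stops one class and starts another after a gap (2-1-2) leaves the row for same number with a different class and is counted as an increase.

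**Step 4. Illustrative size.** Let p be the true share with an increase and f the share of the arm whose count falls and then rises without exceeding baseline. The reported share is p + f. Assume p = 15% and 10%, and equal f in both arms.

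| f | Reported | Ratio | Difference |
|---|---|---|---|
| 0% | 15% v 10% | 1.50 | 5 points |
| 1% | 16% v 11% | 1.45 | 5 points |
| 3% | 18% v 13% | 1.38 | 5 points |
| 5% | 20% v 15% | 1.33 | 5 points |

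With the planned 300 per arm, f = 1%, 3% and 5% are 3, 9 and 15 subjects. All values of f and the 10% are assumptions. Protocol 3.3.1 reports 25/170 (14.7%) for non-dialysis daprodustat participants at 24 weeks. It is no clear guide for the control arm: it prints 18/80 as 14%, whereas 18/80 = 22.5%.

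**The case against.** **The rule may mean something narrower.** The groups in SAP 7.4.2 are defined against baseline, and the title of Table 2.126 says so too. If the rise and the fall in the closing rule are also measured from baseline, it covers only someone above baseline at one time and below it at another, and 3-2-3 and 4-2-3 never trigger it. This reading is possible, but the sentence does not state it. Two programmers could produce different tables, so the wording needs settling either way.

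**Any added drug may be worth counting in a safety display.** That is a coherent measure, and restarting a drug may reflect rising BP. It is not the endpoint defined in either document, and a row labelled as an increase from baseline would not tell the reader that it had been used.

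**Little depends on it.** This stands. SAP 7.4 plans no statistical testing of exploratory endpoints. Worsening of hypertension has its own participant-level tables (3.16 and 3.55), and change in SBP, DBP and MAP is modelled separately.

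**Conclusion.** On its plain wording the closing rule conflicts with the endpoint's definition and adds non-events to the increase row. If they are equally common in both arms, the ratio moves toward 1 and the difference does not change; if they are not, the difference can move either way. The number affected cannot be known from the documents. Only an exploratory, descriptive display is touched; primary and principal secondary inference is not.

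Three stronger inferences are tempting and not supported.

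- *A raised dose is misclassified as no change.* The row is labelled by number and class, and the endpoint is the number of drugs, so the subject sits correctly under that label. What is missing is a display of dose increases, which the broader objective and the collected data would allow.
- *The BP exacerbation definition is faulty because it includes subjects already above the threshold.* SAP 10.6.3 does list "SBP ≥ 180 mmHg and baseline SBP ≥ 180 mmHg", with a matching DBP row at 110 mmHg, but as separate sub-rows. Table 3.35 also reports worst-case vital signs relative to baseline, using the same limits (SAP 10.8.2). If the category rules in SAP 10.6.4, written under laboratory parameters, apply there as its shared shell suggests, a fall from 190 to 182 mmHg is no change. The tested composite still pools these subjects, but altering its definition is a preference.
- *These displays are the trial's only participant-level evidence on worsening hypertension.* Tables 3.16 and 3.55 show otherwise.

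**What to change.** In SAP 7.4.2, replace the closing rule for Table 2.126. Classify a subject as an increase only if the number of BP drugs exceeds the baseline number at some post-baseline time. Otherwise classify by baseline count against last count. This keeps the cautious treatment of a rise followed by a fall and drops only the reverse case. The cost is one sentence and some reprogramming on data already collected, to be done before unblinding.

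Optional: split the row for same number and class to show subjects with a dose increase, using the dose changes recorded under Protocol 7.8. The cost is cleaning of dose and unit records.

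For BP exacerbation, at most add a supportive CMH analysis that leaves out events met only through the absolute threshold in subjects already at or above that threshold at baseline. The main definition can stay.

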7.5. Pharmacogenetics Analyses

Blood samples will be collected as outline in the Schedule of Activities Table in Section [10.2.1](#) for potential future pharmacogenetics (PGx) analysis of the response to daprodustat (GSK1278863). If PGx analysis is pursued, details will be included in a separate RAP.

8. SAFETY ANALYSES

The safety analyses will be based on the Safety population, unless otherwise specified. The details of the planned displays are provided in [Appendix 10: List of Data Displays](#).

| Objectives | Endpoints |
|--|---|
| Safety | |
| 
 To compare the safety and tolerability of daprodustat to placebo | 
 Incidence and severity of AEs and serious adverse events (SAEs) including AEs of special interest and adjudicated MACE (composite of all-cause mortality, non-fatal MI and non-fatal stroke) Reasons for discontinuation of study treatment Absolute values and changes from baseline in laboratory parameters, Blood Pressure (BP) and heart rate (HR) |

8.1. Adjudicated MACE

Adjudicated MACE comprises of all-cause mortality, non-fatal MI and non-fatal stroke.

A summary of the number and percentage of participants having first-occurrence MACE will be provided by treatment group. The number and percentage of the types of events that make up the first occurrence of MACE will also be provided by treatment group.

A summary of all MACE including the number and percentage of participants and number of events (including first and subsequent MACE) by type of event will be provided by treatment group.

Summaries will be produced for all adjudicated MACE and separate summaries for a category of all Adjudicated MACE or Thromboembolic Events or Hospitalization for HF

A listing of all MACE events occurring during the study will be provided and will include treatment, site ID, unique subject ID, select demographic information, event type, event date, and study day.

8.2. Adverse Events Analyses

Adverse events analyses including the analysis of AEs of special interest (AESI), adverse events (AEs), Serious (SAEs) and other significant AEs will be based on GSK Core Data Standards. Adverse events will be coded using the Medical Dictionary for Regulatory Activities (MedDRA) coding dictionary. See Section [10.4.2](#) for AE treatment state definitions.

The analyses of the CEC-adjudicated MACE have been described in Section [8.1](#). However, AE summaries will also include the AEs and SAEs associated with the adjudicated events listed below:

CONFIDENTIAL

205270

- All-cause mortality (CV and non-CV mortality)
- Non-fatal MI
- Non-fatal stroke

For the purpose of AE summaries, the investigator-reported AE details will be used, regardless of the adjudication outcome of the event, unless otherwise specified.

AESIs

Adverse events of special interest and exposure-adjusted AE incidence rate calculation are described in Section [10.6.4](#).

Summaries of AESIs will include the number, percentage, and exposure-adjusted AE incidence rate per 100 person-years of subjects having at least one occurrence, the number of events, the number of subjects by number of occurrences, the characteristics of the AE (serious, drug-related, etc.), outcome, maximum intensity, time to first onset/worsening, and action taken summarized by treatment group. For each count, a subject will be summarized as follows:

- Serious/drug-related/severe/fatal: If any specific AE falls in the respective category, the participant will be counted in that category.
- Outcome: The participant will be counted within a category if there is at least one specific AE in that category.
- Maximum intensity: The specific AE with the maximum intensity will be counted for this purpose. For example, a participant will be counted in the ‘severe’ category if there is at least one specific AE with severe intensity. A participant will be counted in the ‘moderate’ category if there is at least one specific AE with moderate intensity and there is no specific AE with severe intensity.
- Time to first onset/worsening (days): The earliest of onset dates for the specific AE – treatment start + 1

If the AE onset date/AE worsening and/or resolution date is missing or incomplete in the database for any occurrence of the specific AE, time to first onset/worsening and/or duration of the first, second, and third occurrence will be left missing for the participant. These summaries of special interest AEs will be provided for those AEs classified as treatment emergent.

Adverse Events

The number, percentage, and exposure-adjusted AE incidence rate per 100 person-years of participants reporting at least one AE will be provided for each treatment group. These events will be summarized by treatment group, primary system organ class, and preferred term. Similarly, the number and percentage of participants reporting at least one follow-up AE will be summarized by treatment group, primary system organ class, and preferred term.

In addition, all treatment emergent AEs will be summarized by treatment group, primary system organ class, higher level term and preferred term. In addition to generating number and percentage of subjects with treatment emergent SAEs, relative risk and 95% Wald confidence intervals will be presented for each HLT and PT as described in Section [10.6.4](#).

Summaries of all treatment emergent AEs will be produced for the following subgroups - age group, gender, race group, and weight quartile- by treatment group, primary system organ class, and preferred term.

A listing of AE records for all participants who reported AEs will be produced.

The number and percentage of participants reporting the most common treatment emergent AEs (those occurring in $\geq 5\%$ of participants in any treatment group) will be summarized by preferred term and treatment group.

The number and percentage of participants reporting treatment emergent AEs assessed by the investigator to be related to the study drug (termed as drug-related hereafter) will be summarized by treatment group, primary system organ class, and preferred term.

The number and percentage of participants reporting treatment emergent AEs by maximum intensity will be summarized by treatment group, primary system organ class, and preferred term.

The number and percentage of participants reporting treatment emergent drug-related AEs by maximum intensity will be summarized by treatment group, primary system organ class, and preferred term.

A listing of which participants reported specific adverse events will be produced.

The hierarchical relationship between MedDRA SOCs, PTs and verbatim text will be listed for all adverse events.

The number and percentage of participants and the number of occurrences of common non-serious treatment emergent adverse events (those occurring in $\geq 5\%$ of participants in any treatment group) will be summarized by primary system organ class, preferred term, and treatment group.

CONFIDENTIAL

205270

The number and percentage of participants with treatment emergent non-serious drug-related adverse events will be summarized by primary system organ class, preferred term, and treatment group and separately by overall frequency

Serious and Other Significant Adverse Events

The number and percentage of participants and the number of occurrences of treatment emergent SAEs will be provided for each treatment group. These events will be summarized by treatment group, primary system organ class, and preferred term. Follow-up SAEs will be summarized similarly.

Additionally, a tabular display of exposure-adjusted AE incidence rate per 100 person-years of participants reporting at least one SAE will be produced by treatment group, primary system organ class, and preferred term.

All treatment emergent SAEs will also be summarized by treatment group, primary system organ class, higher level term and preferred term. In addition to generating number and percentage of subjects with TE SAEs, relative risk and 95% Wald confidence intervals will be presented for each HLT and PT as described in Section 10.6.4.

A listing of reasons for considering as a SAE will be produced for all treatment emergent SAEs.

The number and percentage of participants with treatment emergent drug-related SAEs will be summarized by treatment group, primary system organ class and preferred term.

The number, percentage, and exposure-adjusted AE incidence rate per 100 person-years of participants with fatal AEs will be provided for each treatment group. These events will be summarized by treatment group, primary system organ class, and preferred term.

Additionally, the number and percentage of participants with treatment emergent serious, fatal and non-fatal, drug-related AEs will be summarized by treatment group and overall frequency.

A listing of treatment emergent fatal SAE records and a listing of treatment emergent non-fatal SAE records will be provided.

The number, percentage, and exposure adjusted AE incidence rate per 100 person-years of participants reporting treatment emergent AEs leading to discontinuation of randomized treatment will be summarized by treatment group, primary system organ class, and preferred term.

A listing of treatment emergent AEs leading to discontinuation of randomized treatment will be provided.

CONFIDENTIAL

205270

A listing of other significant adverse events will be produced. Other significant adverse events are events that are not reported as fatal or serious but represent ICH-defined ‘Other significant adverse events’ (i.e., marked haematological and other laboratory abnormalities or led to an intervention, dose reduction, or significant additional concomitant therapy). For this study, other significant AEs will be defined as non-fatal non-serious AEs resulting in an action taken with study treatment of either ‘dose interrupted/delayed’ or ‘dose reduced’.

